### **Eastern Cooperative Oncology Group performance status**

The ECOG data will be summarized by treatment arm for Safety analysis set. Shifts in ECOG performance status from baseline to worst on-treatment performance status will be summarized by treatment group. Missing category will also be included.

A listing will also be provided for ECOG performance status.

## **18 Benefit Risk Assessment**

Not applicable.

Appendix 1 Important Protocol Deviations

| Important Protocol Deviations   | Clinically Important PD (Y/N) | Can be programmed or not (Y/N) |
|---|-------------------------------|--------------------------------|
| Inclusion criteria not fulfilled  |                               |                                |
| Inclusion criteria not fulfilled (#02): No histologically or cytologically confirmed diagnosis of SCCHN   | Y                             | Y                              |
| Inclusion criteria not fulfilled (#03): No recurrent and/or metastatic SCCHN not suitable for local therapy   | Y                             | Y                              |
| Inclusion criteria not fulfilled (#06): ECOG performance status of 0 or 1   | Y                             | Y                              |
| Exclusion criteria fulfilled  |                               |                                |
| Exclusion criteria fulfilled (ex#01): Prior systemic chemotherapy, except if given as part of multimodal treatment for locally advanced disease that was completed within 6 months before trial entry. (Amendment)  | Y                             | Y                              |
| Exclusion criteria fulfilled (ex#03): Previous treatment with monoclonal antibody or signal transduction inhibitors targeting EGFR.   | Y                             | Y                              |
| Exclusion criteria fulfilled (ex#04): Nasopharyngeal carcinoma.   | Y                             | Y                              |
| All patients who don't fulfill other inclusion criteria or fulfill exclusion criteria.  | N                             | Y                              |
| Other Protocol Deviations   |                               |                                |
| Randomization error: Incorrect treatment group allocation, different to assignment at randomization   | Y                             | Y                              |
| Randomization error: Subject randomized but did not receive any study treatment   | Y                             | Y                              |
| Randomization error: Stratification error   | N                             | Y                              |
| Use of prohibited medication: Additional concurrent chronic systemic immune treatment, chemotherapy, radiotherapy (with exceptions), hormone treatment for treatment of cancer (with exceptions), traditional Chinese medication with approval for use as anticancer treatment or any other investigational agent | Y                             | N                              |
| Tumor assessment: missed one or more locations on tumor assessment  | N                             | N                              |
| Tumor evaluation error by investigator according to RECIST version 1.1  | N                             | N                              |
| Tumor assessment delay: Out of window visit equal or above 3 weeks  | N                             | Y                              |

| Important Protocol Deviations  | Clinically Important PD (Y/N) | Can be programmed or not (Y/N) |
|--|-------------------------------|--------------------------------|
| Continuation on cetuximab treatment when withdrawal criteria met: Occurrence of pregnancy during trial treatment   | N                             | N                              |
| Continuation on cetuximab treatment when withdrawal criteria met: Occurrence of PD according to RECIST version 1.1   | N                             | N                              |
| Continuation on cetuximab/chemotherapy treatment if occurrence of an exclusion criterion that is clinically relevant and affects the subject's safety and discontinuation is considered necessary by the Investigator and/or Sponsor | N                             | N                              |
| Continuation on cetuximab/chemotherapy treatment if occurrence of AEs and discontinuation of trial treatment is desired or considered necessary by the Investigator and/or the subject   | N                             | N                              |
| Continuation on chemotherapy if a delay in chemotherapy treatment of more than 21 days due to toxicity   | N                             | Y                              |
| Continuation on cisplatin if occurrence of more than 2 dose reductions of cisplatin  | N                             | N                              |
| Continuation on carboplatin if more than 1 dose reduction of carboplatin   | N                             | N                              |
| Continuation on 5-FU if occurrence of more than 2 dose reductions of 5-FU  | N                             | N                              |
| Continuation on chemotherapy if occurrence of any other criteria requiring discontinuation of chemotherapy.  | N                             | N                              |
| Continuation on chemotherapy if occurrence of AEs, if discontinuation of chemotherapy is desired or considered necessary by the subject and/or Investigator.   | N                             | N                              |
| Continuation on cetuximab treatment if more than 2 consecutive cetuximab infusions withdrawn due to toxicity   | N                             | N                              |
| Continuation on cetuximab treatment if occurrence of any Grade 4 toxicities related to cetuximab   | N                             | N                              |
| Continuation on cetuximab treatment if a fourth occurrence of a Grade 3 skin toxicity related to cetuximab despite appropriate dose reduction  | N                             | N                              |
| Continuation on cetuximab treatment if occurrence of at least Grade 3 infusion-related reaction (excluding fever) related to cetuximab   | N                             | N                              |
| Continuation on cetuximab treatment if a second episode of any cetuximab infusion-related reaction following a 50% reduction in infusion rate  | N                             | N                              |
| Continuation on cetuximab treatment if diagnosis of interstitial lung disease during the trial   | N                             | N                              |
| Continuation on cetuximab treatment if occurrence of AEs, if discontinuation of cetuximab is desired or considered necessary by the subject and/or Investigator.   | N                             | N                              |
| IP/Non-IP compliance: Received less than 3 full consecutive cetuximab infusions as specified in the protocol (a full dose is defined as 90% of planned dose)   | N                             | N                              |
| IP/Non-IP compliance: More than 24 days off cetuximab treatment  | N                             | N                              |
| IP/Non-IP compliance: Drug overdose – Actual dose is >10% greater than Planned dose  | N                             | Y                              |

### Appendix 2 Inclusion Criteria 3

| Inclusion criteria 3 in protocol version 1                                    | Inclusion criteria 3 in protocol version 2   |
|---|--|
| Recurrent and/or metastatic SCCHN, not suitable for local-regional treatment. | Recurrent and/or metastatic SCCHN, not suitable for local-regional treatment. Subjects with recurrent disease only (no metastases) must have received prior radiotherapy (as adjuvant treatment after surgery or as treatment for locally advanced SCCHN) as part of “loco-regional treatment”, and the radiotherapy must have been completed more than 6 months before screening imaging. |

**Appendix 3 NCI-CTCAE v4.03 Grades for Laboratory Parameters**

| Laboratory Parameter      | CTCAE grade is defined based on lab value only | CTCAE v4.03 term           | NCICTC Definition   |   |   |  |         |
|---------------------------|--|----------------------------|---|---|---|--|---------|
|                           |  |                            | Grade 1   | Grade 2   | Grade 3   | Grade 4  | Grade 5 |
| Hematology         |  |                            |   |   |   |  |         |
| Erythrocytes (10E12/L)    | No   |                            |   |   |   |  |         |
| Hemoglobin (g/L) High     | Yes  | Hemoglobin increased       | Increase in >0 - 2 gm/dL above ULN or above baseline if baseline is above ULN | Increase in >2 - 4 gm/dL above ULN or above baseline if baseline is above ULN | Increase in >4 gm/dL above ULN or above baseline if baseline is above ULN |  |         |
| Hemoglobin (g/L) Low      | Yes  | Anemia                     | Hemoglobin (Hgb) <LLN - 10.0 g/dL; <LLN - 6.2 mmol/L; <LLN - 100 g/L          | Hgb <10.0 - 8.0 g/dL; <6.2 - 4.9 mmol/L; <100 - 80g/L                         | Hgb <8.0 g/dL; <4.9 mmol/L; <80 g/L; transfusion indicated                | Life-threatening consequences; urgent intervention indicated | Death   |
| Leukocytes (10E9/L)       | Yes  | White blood cell decreased | <LLN - 3000/mm3; <LLN - 3.0 x 10e9 /L   | <3000 2000/mm3; <3.0 - 2.0 x 10e9 /L  | <2000 1000/mm3; <2.0 - 1.0 x 10e9 /L                                      | <1000/mm3; <1.0 x 10e9 /L                                    | -       |
| Lymphocytes (10E9/L) High | Yes  | Lymphocyte count increased | -   | >4000/mm3 20,000/mm3  | >20,000/mm3   | -  | -       |
| Lymphocytes (10E9/L) Low  | Yes  | Lymphocyte count decreased | <LLN - 800/mm3; <LLN - 0.8 x 10e9/L   | <800 - 500/mm3; <0.8 - 0.5 x 10e9 /L  | <500 - 200/mm3; <0.5 - 0.2 x 10e9 /L                                      | <200/mm3; <0.2 x 10e9 /L                                     | -       |
| Neutrophils (10E9/L)      | Yes  | Neutrophil count decreased | <LLN 1500/mm3; <LLN - 1.5 x 10e9 /L   | <1500 1000/mm3; <1.5 - 1.0 x 10e9 /L  | <1000 500/mm3; <1.0 - 0.5 x 10e9 /L                                       | <500/mm3; <0.5 x 10e9 /L                                     | -       |

| Laboratory Parameter             | CTCAE grade is defined based on lab value only | CTCAE v4.03 term                     | NCICTC Definition   |   |   |   |         |  |
|----------------------------------|--|--------------------------------------|---|---|---|---|---------|--|
|                                  |  |                                      | Grade 1   | Grade 2   | Grade 3   | Grade 4   | Grade 5 |  |
| Monocytes (10E9/L)               | No   |                                      |   |   |   |   |         |  |
| Eosinophils (10E9/L)             | No   |                                      |   |   |   |   |         |  |
| Basophils (10E9/L)               | No   |                                      |   |   |   |   |         |  |
| Platelet (10E9/L)                | Yes  | Platelet count decreased             | <LLN
75,000/mm  ;
<LLN - 75.0 x
10e9/L | <75,000
50,000/mm  ;
<75.0 - 50.0 x
10e9/L | <50,000
25,000/mm  ;
<50.0 - 25.0 x
10e9/L | -
-
<25,000/mm  ;
<25.0 x 10e9/L |         |  |
| Biochemistry              |  |                                      |   |   |   |   |         |  |
| Creatinine (umol/L)              | Yes  | Creatinine increased                 | >1 - 1.5 x
baseline; >ULN -
1.5 x ULN                 | >1.5 - 3.0 x
baseline; >1.5 -
3.0 x ULN                   | >3.0 baseline;
>3.0 - 6.0 x ULN                              | >6.0 x ULN  |         |  |
| Alanine Aminotransferase (U/L)   | Yes  | Alanine aminotransferase increased   | >ULN - 3.0 x ULN  | >3.0 - 5.0 x ULN  | >5.0 - 20.0 x ULN   | >20.0 x ULN   |         |  |
| Aspartate Aminotransferase (U/L) | Yes  | Aspartate aminotransferase increased | >ULN - 3.0 x ULN  | >3.0 - 5.0 x ULN  | >5.0 - 20.0 x ULN   | >20.0 x ULN   |         |  |
| Gamma Glutamyl Transferase (U/L) | Yes  | GGT increased                        | >ULN - 2.5 x ULN  | >2.5 - 5.0 x ULN  | >5.0 - 20.0 x ULN   | >20.0 x ULN   |         |  |
| Total Bilirubin (umol/L)         | Yes  | Blood bilirubin increased            | >ULN - 1.5 x ULN  | >1.5 - 3.0 x ULN  | >3.0 - 10.0 x ULN   | >10.0 x ULN   |         |  |
| Direct Bilirubin (umol/L)        | Yes  | Blood bilirubin increased            | >ULN - 1.5 x ULN  | >1.5 - 3.0 x ULN  | >3.0 - 10.0 x ULN   | >10.0 x ULN   |         |  |
| Lipase (IU/L)                    | Yes  | Lipase increased                     | >ULN - 1.5 x ULN  | >1.5 - 2.0 x ULN  | >2.0 - 5.0 x ULN  | >5.0 x ULN  |         |  |

| Laboratory Parameter         | CTCAE grade is defined based on lab value only | CTCAE v4.03 term               | NCICTC Definition   |  |  |   |         |
|------------------------------|--|--------------------------------|---|--|--|---|---------|
|                              |  |                                | Grade 1   | Grade 2  | Grade 3  | Grade 4   | Grade 5 |
| Amylase (IU/L)               | Yes  | Serum amylase increased        | >ULN - 1.5 x ULN  | >1.5 - 2.0 x ULN   | >2.0 - 5.0 x ULN   | >5.0 x ULN  | -       |
| Total Protein (G/L)          | No   |                                |   |  |  |   |         |
| Albumin (g/L)                | Yes  | Hypoalbuminemia                | <LLN - 3 g/dL; <LLN - 30 g/L  | <3 - 2 g/dL; <30 - 20 g/L  | <2 g/dL; <20 g/L   | Life-threatening consequences; urgent intervention indicated    | Death   |
| Alkaline phosphatase (IU/L)  | Yes  | Alkaline phosphatase increased | >ULN - 2.5 x ULN  | >2.5 - 5.0 x ULN   | >5.0 - 20.0 x ULN  | >20.0 x ULN   | -       |
| Glucose (mmol/L) High        | Yes  | Hyperglycemia                  | Fasting glucose value >ULN - 160 mg/dL; Fasting glucose value >ULN - 8.9 mmol/L | Fasting glucose value >160 - 250 mg/dL; Fasting glucose value >8.9 - 13.9 mmol/L | >250 - 500 mg/dL; >13.9 - 27.8 mmol/L; hospitalization indicated | >500 mg/dL; >27.8 mmol/L; life-threatening consequences         | Death   |
| Glucose (mmol/L) Low         | Yes  | Hypoglycemia                   | <LLN - 55 mg/dL; <LLN - 3.0 mmol/L  | <55 - 40 mg/dL; <3.0 - 2.2 mmol/L  | <40 - 30 mg/dL; <2.2 - 1.7 mmol/L                                | <30 mg/dL; <1.7 mmol/L; life-threatening consequences; seizures | Death   |
| Blood Urea Nitrogen (mmol/L) | No   |                                |   |  |  |   |         |
| Uric Acid (umol/L)           | Yes  | Hyperuricemia                  | >ULN - 10 mg/dL (0.59 mmol/L) without physiologic consequences                  | -  | >ULN - 10 mg/dL (0.59 mmol/L) with physiologic consequences      | >10 mg/dL; >0.59 mmol/L; life-threatening consequences          | Death   |

| Laboratory Parameter            | CTCAE grade is defined based on lab value only | CTCAE v4.03 term | NCICTC Definition  |  |  |                                |   |       |
|---------------------------------|--|------------------|--|--|--|--------------------------------|---|-------|
|                                 |  |                  | Grade 1  | Grade 2  | Grade 3  | Grade 4                        | Grade 5   |       |
| Sodium (mmol/L) High            | Yes  | Hypernatremia    | >ULN - 150 mmol/L  | >150 mmol/L  | >155 mmol/L; hospitalization indicated   | 155 - 160 mmol/L               | >160 mmol/L; life-threatening consequences  | Death |
| Sodium (mmol/L) Low             | Yes  | Hyponatremia     | <LLN - 130 mmol/L  | -  | <130 mmol/L  | 120 - 130 mmol/L               | <120 mmol/L; life-threatening consequences  | Death |
| Potassium (mmol/L) High         | Yes  | Hyperkalemia     | >ULN - 5.5 mmol/L  | >5.5 - 6.0 mmol/L  | >6.0 - 7.0 mmol/L; hospitalization indicated   | 7.0 - 8.0 mmol/L               | >7.0 mmol/L; life-threatening consequences  | Death |
| Potassium (mmol/L) Low          | Yes  | Hypokalemia      | <LLN - 3.0 mmol/L  | <LLN - 3.0 mmol/L; symptomatic; intervention indicated   | <3.0 - 2.5 mmol/L; hospitalization indicated   | 2.5 - 3.0 mmol/L               | <2.5 mmol/L; life-threatening consequences  | Death |
| Chloride (mmol/L)               | No   |                  |  |  |  |                                |   |       |
| Calcium (mmol/L)                | No   |                  |  |  |  |                                |   |       |
| Corrected Calcium (mmol/L) High | Yes  | Hypercalcemia    | Corrected serum calcium of >ULN - 11.5 mg/dL; >ULN - 2.9 mmol/L; Ionized calcium >ULN - 1.5 mmol/L | Corrected serum calcium of >11.5 - 12.5 mg/dL; >2.9 - 3.1 mmol/L; Ionized calcium >1.5 - 1.6 mmol/L; symptomatic | Corrected serum calcium of >12.5 - 13.5 mg/dL; >3.1 - 3.4 mmol/L; Ionized calcium >1.6 - 1.8 mmol/L; hospitalization indicated | 13.5 - 14.5 mg/dL; >3.4 mmol/L | Corrected serum calcium of >13.5 mg/dL; >3.4 mmol/L; Ionized calcium >1.8 mmol/L; life-threatening consequences | Death |

| Laboratory Parameter    | CTCAE grade is defined based on lab value only | CTCAE v4.03 term | NCICTC Definition   |   |   |  |         |
|-------------------------|--|------------------|---|---|---|--|---------|
|                         |  |                  | Grade 1   | Grade 2   | Grade 3   | Grade 4  | Grade 5 |
| Calcium (mmol/L) Low    | Yes  | Hypocalcemia     | Corrected serum calcium of <LLN - 8.0 mg/dL; <LLN - 2.0 mmol/L; ionized calcium <LLN - 1.0 mmol/L | Corrected serum calcium of <8.0 - 7.0 mg/dL; <2.0 - 1.75 mmol/L; ionized calcium <1.0 - 0.9 mmol/L; symptomatic | Corrected serum calcium of <7.0 - 6.0 mg/dL; <1.75 - 1.5 mmol/L; ionized calcium <0.9 - 0.8 mmol/L; hospitalization indicated | Corrected serum calcium of <6.0 mg/dL; <1.5 mmol/L; ionized calcium <0.8 mmol/L; life-threatening consequences | Death   |
| Magnesium (mmol/L) High | Yes  | Hypermagnesemia  | >ULN - 3.0 mg/dL; >ULN - 1.23 mmol/L  | -   | >3.0 - 8.0 mg/dL; >1.23 - 3.30 mmol/L   | >8.0 mg/dL; >3.30 mmol/L; life-threatening consequences  | Death   |
| Magnesium (mmol/L) Low  | Yes  | Hypomagnesemia   | <LLN - 1.2 mg/dL; <LLN - 0.5 mmol/L   | <1.2 - 0.9 mg/dL; <0.5 - 0.4 mmol/L   | <0.9 - 0.7 mg/dL; <0.4 - 0.3 mmol/L   | <0.7 mg/dL; <0.3 mmol/L; life-threatening consequences   | Death   |

**21**

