7.4.3 Clinical Laboratory Assessments

Blood and urine samples will be collected for hematology, biochemistry, electrolytes, and urinalysis following the timing noted in the Schedule of Assessments (Table 1.1) and will include the following mentioned below in Table 7.1. The results of all safety laboratory parameters must be available within 3 days before start of next chemotherapy cycle.

Table 7.1 Standard Safety Laboratory Parameters

Category	Parameters
Hematology	hemoglobin, red blood cell count, white blood cell count and differential count, platelet count
Biochemistry	creatinine, aspartate aminotransferase, alanine aminotransferase, gamma-glutamyl transferase, total bilirubin (including direct bilirubin if total bilirubin abnormal), total protein, albumin, alkaline phosphatase, glucose, blood urea, uric acid
Electrolytes	sodium, potassium, chloride, calcium, magnesium,
Urinalysis*	pH value, specific gravity, protein, glucose, red blood cell, white blood cell
Urinalysis	dipstick will be followed by microscopic examination if results are abnormal.

69/131

All samples should be clearly identified. Blood samples will be collected after fasting for at least 8 hours. All laboratory assessments will be performed at local laboratories and will comply with local requirements. Analysis of additional laboratory parameters is at the discretion of the Investigator. Viral serology tests will be performed if clinically indicated (see Section 7.2.4).

At the screening visit, female subjects of childbearing potential including those who have had tubal ligation must additionally have a blood pregnancy test performed within 7 days before the first dose of trial treatment. Pregnancy testing must be repeated regularly throughout the trial if required by local legislation.

All laboratory test results obtained (including any potential repeat tests) must be documented in the eCRF.

Any laboratory result leading to an interruption or dose reduction of trial treatments will be considered as an untoward medical occurrence and therefore has to be documented as an AE (see Section 7.4.1.1).

The Sponsor should receive a list of laboratory normal ranges before shipment of trial drug. Any change in laboratory normal ranges during the trial should be forwarded to the Sponsor/designee.

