8.5.4 Analysis of Safety

Safety analyses will be performed according to the as-treated principle. Any TEAEs will be summarized, i.e., those events that emerge during treatment having been absent pre-treatment, or worsen relative to the pre-treatment state and with onset dates occurring within the first dosing day of trial treatment until 30 days after the last dose of trial treatment. No formal statistical comparisons are planned.

The extent of exposure for cetuximab, cisplatin or carboplatin, and 5-FU will be characterized by duration (weeks), cumulative dose, dose intensity, relative dose intensity (actual dose given/planned dose), number of dose reductions, and number of dose delays.

AEs will be coded according to the current Medical Dictionary for Regulatory Affairs (MedDRA). The severity of AEs will be graded using CTCAE toxicity grades. The incidence and type of AEs, SAEs, trial treatment-related AEs and SAEs, trial treatment-related AEs by CTCAE toxicity grade, CTCAE Grade 3 and 4 AEs, trial treatment-related CTCAE Grade 3 and 4 AEs, AEs leading to death, AEs leading to discontinuation of trial treatment, will be summarized in total and for each treatment arm according to the MedDRA system organ class and MedDRA preferred terms. Missing classifications concerning trial treatment relationship will be considered as related to the trial treatment.

All deaths, deaths within 60 days after date of first dose of trial treatment and deaths within 30 days after last dose of trial treatment as well as reasons for deaths will be tabulated.

Laboratory results will be classified according to the CTCAE (version 4.03) when applicable. The worst on trial grade after date of first dose of trial treatment will be summarized. Shifts in toxicity grading from treatment start to highest grade will be displayed. Results for variables that were not part of the CTCAE (version 4.03) will be presented as below, within, and above the normal limits of the local laboratory. Only subjects with post-baseline laboratory values will be included in these analyses. The last measurement before trial treatment will serve as the baseline measurement.

Vital signs (temperature, heart rate, blood pressure, respiratory rate) will be descriptively presented.

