#### **NCI-CTCAE grades available:**

The worst on-trial grade, i.e. the highest CTCAE grade after the first dose of trial treatment will be summarized by parameter as follows:

- Number and percentage of subjects with grade  $\geq 0$ .
- Number and percentage of subjects with grade  $\geq 3$ .
- Number and percentage of subjects with grade = 4.

Tables will summarize, separately for hematology and biochemistry parameters, the shift from baseline grade to worst on-treatment grade by parameter and treatment group.

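### SAP Appendix 3 grades direct bilirubin under the same term and ULN multiples as total bilirubin, adding a second line for one toxicity that rests mainly on subjects already selected for abnormal total bilirubin

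*SAP*

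**What the plan says.** SAP Appendix 3 has two bilirubin rows, "Total Bilirubin (umol/L" and "Direct Bilirubin (umol/L". Both are marked Yes for grading on the laboratory value alone. Both carry the term "Blood bilirubin increased" and the same four grade bands, with cut-offs at 1, 1.5, 3 and 10 times ULN.

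The two tests are not collected alike. Protocol Section 7.4.3, Table 7.1, requires "total bilirubin (including direct bilirubin if total bilirubin abnormal", and the laboratory footnote to Protocol Table 1.1 sets the same condition. Section 7.4.3 also leaves room for extra tests: "Analysis of additional laboratory parameters is at the discretion of the Investigator".

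SAP Section 17.3 reports graded parameters one by one: "The worst on-trial grade, i.e. the highest CTCAE grade after the first dose of trial treatment will be summarized by parameter as follows". The lines are grade 0 or higher, grade 3 or higher, and grade 4. It also tabulates "the shift from baseline grade to worst on-treatment grade by parameter and treatment group". It has no rule for a test that is done only conditionally.

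Two denominator statements apply. Protocol Section 8.5.4 says of the laboratory analyses: "Only subjects with post-baseline laboratory values will be included in these analyses". SAP Section 11 takes proportions over the whole analysis set unless otherwise stated, with missing values shown as a category.

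**The concern.** Whether a subject has a direct bilirubin value depends largely on whether total bilirubin was already abnormal. That is a post-randomization outcome and may differ between arms. A percentage taken among tested subjects therefore does not estimate how often the abnormality occurs in the arm, and it can hide a difference between arms.

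The shift table has a related gap. A subject with normal total bilirubin before treatment has no required direct value, so there is no baseline grade to shift from.

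Both rows also share one toxicity name, yet each is graded against its own local ULN. One blood sample can thus yield two different grades of what reads as the same toxicity. A reader of the safety tables could take the direct bilirubin line for the trial's bilirubin toxicity rate.

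**Working it through.** The documents give no figure on this point, so there is none to reproduce. The cut-offs are from Appendix 3, and the planned size (240 subjects at 2:1, so 160 and 80) is from the synopsis. All rates, direct shares and ULN ratios below are assumptions for illustration.

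**1. Row comparison.** Term, grading flag and cut-offs are identical for the two rows.

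**2. Effect of the denominator.** Let f be the share of subjects tested and q the share of tested subjects with direct bilirubin above ULN.

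- Tested-only denominator: percentage = q.
- Whole analysis set: percentage = f × q.
- Ratio of the two = 1/f.

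With q = 60%:

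| f | Tested of 160 | Tested-only | Whole set | Ratio |
|---|---|---|---|---|
| 10% | 16 | 60% | 6% | 10 |
| 20% | 32 | 60% | 12% | 5 |
| 40% | 64 | 60% | 24% | 2.5 |

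For q from 30% to 90% over the same f, tested-only figures run from 30% to 90% and whole-set figures from 3% to 36%.

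**3. Arm comparison.** Suppose 32 of 160 in Arm A and 8 of 80 in Arm B are tested, and half of those tested are above ULN. Tested-only gives 16/32 = 50% against 4/8 = 50%. The whole set gives 16/160 = 10% against 4/80 = 5%. The tested-only line hides a twofold difference.

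**4. Under-counting with the whole set.** Let r be the share of untested subjects whose direct bilirubin is above ULN. The full-population value is f × q + (1 − f) × r. At f = 20% and q = 60%:

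- r = 0%: 0.2 × 0.6 + 0.8 × 0 = 12.0%;
- r = 5%: 0.2 × 0.6 + 0.8 × 0.05 = 16.0%.

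The reported figure is 12.0% in both cases.

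**5. Grade disagreement.** Direct multiple of ULN = direct share × total multiple ÷ (direct ULN / total ULN). Take total bilirubin at 1.3 × ULN, which is Grade 1:

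| Direct share | ULN ratio | Direct multiple | Direct grade |
|---|---|---|---|
| 70% | 0.2 | 0.7 × 1.3 / 0.2 = 4.55 | 3 |
| 70% | 0.4 | 0.7 × 1.3 / 0.4 = 2.28 | 2 |
| 40% | 0.4 | 0.4 × 1.3 / 0.4 = 1.30 | 1 |
| 30% | 0.2 | 0.3 × 1.3 / 0.2 = 1.95 | 2 |
| 30% | 0.4 | 0.3 × 1.3 / 0.4 = 0.98 | none |

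The direct grade can be higher than, equal to or lower than the total bilirubin grade.

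**6. Baseline.** Inclusion criterion 8 allows total bilirubin up to 2 × ULN, so some subjects will have a direct value before treatment. If most enter with normal total bilirubin, which is an assumption, most have no required baseline value.

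**The case against.** A reader might infer that the reported percentages necessarily come from the selected subset. The text does not compel that. Protocol Section 8.5.4 refers to post-baseline laboratory values without saying values of the parameter in question. Read as any laboratory value, it keeps nearly all treated subjects in the denominator. The SAP Section 11 rule also avoids the inflation. A rate of grade 1 or higher is not a line in the worst-grade summary and would emerge only from the shift table. The line for grade 0 or higher would show how few subjects were graded. All of this stands, so the inflation is conditional.

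A reader might also infer that direct bilirubin always grades higher than total bilirubin. The documents give no ULN for either test and no direct share, and laboratories are local. Step 5 shows that even the direction is open.

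Nor do the documents support saying that bilirubin toxicity goes unmeasured. Total bilirubin is a required test with its own graded row, the direct line does not replace it, and investigators grade adverse events separately. It would also be too strong to say that direct bilirubin is never measured when total bilirubin is normal, since extra tests are permitted.

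What the objection does not remove is the duplicate line: same term, same multiples, conditional collection, and no rule in Section 17.3 to handle it.

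**Conclusion.** The point holds as a minor one. Following the SAP as written produces a second worst-grade and shift line for the same toxicity term. That line rests mainly on subjects already found to have abnormal total bilirubin, probably has a mostly missing baseline, and may disagree with the total bilirubin grade in either direction.

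If the Protocol Section 8.5.4 restriction is applied per parameter, percentages are inflated by 1/(share tested), which is 10-, 5- and 2.5-fold at assumed shares of 10%, 20% and 40%. Under the SAP Section 11 rule there is no inflation, only some under-counting if untested subjects have raised values.

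The consequence is limited to descriptive safety tables for which no formal comparison is planned. The primary endpoint, sample size and error rates are unaffected.

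**What to change.** Two small edits to the SAP are needed:

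1. In Appendix 3, change the direct bilirubin row from Yes to No and remove its term and grade bands.
2. In Section 17.3, add one sentence stating that direct bilirubin is listed only, that it is left out of the summary and shift tables for both graded and ungraded parameters, and that the bilirubin toxicity term is graded on total bilirubin alone.

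The first edit is not enough alone. Section 17.3 sends ungraded biochemistry parameters to low/normal/high summaries and shift tables, where the same selected subset would reappear.

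The SAP already has precedents. Section 17.3 makes the hematology differential percentages listing-only, and Appendix 3 leaves the plain calcium row ungraded while grading hypercalcemia on corrected calcium.

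The cost is one table row and one sentence, with slightly fewer outputs. The downside is that direct bilirubin is then available only in listings. Those listings already show the value, the local normal range and the low/normal/high indicator. If the sponsor prefers to keep a table, the row needs a distinct label, a stated denominator and the number tested.
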